7.2.5.3. Dose Delays for Reasons Not Related to Study Treatment

Dosing interruptions of either study drug of ≤ 1 week are also permitted for reasons not related to study treatment (for example, minor surgery, unrelated medical events, patient vacation, and/or holidays). The reason for interruption should be documented on the CRF.

7.3. Method of Assignment to Treatment

This study is open-label for Phase 1a and Phase 1b. Before each patient's enrollment into the study, an eligibility check must be conducted between the investigational site and the Lilly clinical research personnel to confirm that each patient meets all enrollment criteria. Upon confirmation of eligibility, the sponsor will confirm the dose and identification number assignment and cohort/expansion arm for each patient.

For Phase 1a, if investigators have eligible patients who have consented concurrently, more than 3 patients may be entered at a particular dose level provided that accrual has not ceased due to excessive toxicity. This enrollment procedure is allowed because of the advanced disease state of this patient population and the screening involved in defining eligibility. This event should be approved by the sponsor following discussions with the investigators.

7.4. Blinding

Not applicable. This is an open-label study.

7.5. Concomitant Therapy

No other therapy, including routine use of growth factors or experimental medications (for example, immunotherapy or other not approved medication) will be permitted while the patients are on the study. Growth factors and erythropoietin are allowed per American Society of

Clinical Oncology or National Comprehensive Cancer Network guidelines. Granulocyte colony-stimulating factors must be discontinued at least 24 hours prior to the start of the next cycle of treatment. Transfusions are permitted. Patients may receive prophylactic steroids (such as, prednisolone, methylprednisolone or dexamethasone; see below for limits) to prevent transfusion reactions.

Any concurrent antineoplastic therapy (ie, chemotherapy, hormonal therapy, immunotherapy, extensive, nonpalliative radiation therapy, or standard or investigational agents for treatment of pancreatic cancer) will not be allowed unless outlined elsewhere. Any disease progression requiring other forms of specific antitumor therapy will necessitate early discontinuation from the study. Appropriate documentation for all forms of premedications, supportive care, and concomitant medications must be captured on the CRF. Replacement hormonal therapy initiated before study entry will be allowed.

Immunosuppressive medications will not be allowed including, but not limited to systemic corticosteroids at doses exceeding 10 mg/day of prednisone or equivalent, methotrexate, azathioprine, and tumor necrosis factor- α blockers. Use of immunosuppressive medications for the management of investigational product-related AEs, in patients with contrast allergies or for treatment of nonautoimmune conditions (eg, delayed-type hypersensitivity reaction caused by a contact allergen) is acceptable. Patients are also permitted the use of topical, ocular, intra-articular, intranasal, and inhalational corticosteroids (with minimal systemic absorption) unless outlined elsewhere. Live attenuated vaccines within 30 days of durvalumab dosing are not permitted (ie, 30 days prior to the first dose, during treatment with durvalumab and for 30 days post discontinuation of durvalumab). Inactivated vaccines, such as the injectable influenza vaccine, are permitted. Seasonal influenza vaccines for injection are generally killed virus vaccines and are allowed; however, intranasal influenza vaccines (eg, FluMist[®]) are live attenuated vaccines and are not allowed (see Section 6.1.3).

Patients should receive full supportive care during the trial. Concomitant palliative and supportive care for disease-related symptoms (including bisphosphonates and RANK-L inhibitors) is allowed if initiated prior to first dose of study therapy. Prior palliative radiotherapy must have been completed at least 2 weeks prior to enrollment. The potential for overlapping toxicities with radiotherapy and durvalumab currently is not known. Therefore, palliative radiotherapy is not recommended while receiving durvalumab.

All concomitant medications should be recorded throughout the patient's participation in the study.

7.5.1. Restrictions during Study

Females of childbearing potential who are sexually active with a nonsterilized male partner must use effective contraception from screening, and must agree to continue using such precautions for 6 months following the last infusion of durvalumab; cessation of birth control after this point should be discussed with a responsible physician. Male partners of a female patient must use male condom plus spermicide throughout this period. If a barrier method of contraception is

used, 2 methods must be used as outlined in [Table CXAD.7.3](#). Periodic abstinence, the rhythm method, and the withdrawal method are not acceptable methods of birth control.

- Females of childbearing potential are defined as those who are not surgically sterile (ie, bilateral tubal ligation, bilateral oophorectomy, or complete hysterectomy) or postmenopausal (defined as 12 months with no menses without an alternative medical cause).
- Patients must use **2 acceptable methods** of effective contraception as described in [Table CXAD.7.3](#).
- Nonsterilized males who are sexually active with a female partner of childbearing potential must use **2 acceptable methods** of effective contraception (see [Table CXAD.7.3](#)) from Day 1 and for 6 months after receipt of the final dose of durvalumab.

Table CXAD.7.3 Acceptable Methods of Contraception

Barrier Methods	Intrauterine Device Methods	Hormonal Methods
Male condom plus spermicide	Copper T	Implants
Cap plus spermicide	Progesterone T ^a	Hormone shot or injection
Diaphragm plus spermicide	Levonorgestrel-releasing intrauterine system (eg, Mirena [®]) ^a	Combined pill Minipill Patch

^a Also considered a hormonal method.

Patients should not donate blood while participating in this study or for 3 months after discontinuation of study treatment.

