5.5. General Introduction to LY2510924 and Durvalumab

5.5.1. LY2510924

5.5.1.1. LY2510924 Chemokines, SDF-1, and CXCR4

Chemokines are important molecules that guide the migration of cells from one tissue to another. The CXCR4 is a transmembrane G-protein–coupled receptor. CXCR4 and its only known ligand, α -chemokine stromal-cell derived factor-1 (SDF-1) are believed to play an important role in the regulation of organ-specific metastasis, as well as tumor growth, invasion, survival, and angiogenesis (Balkwill 2004; Peng et al. 2015). The CXCR4/SDF-1 axis is involved in the migration of hematopoietic stem cells and lymphocytes, and both are required for normal murine fetal development (Balkwill 2004). SDF-1 is expressed widely throughout the body, and SDF-1 concentrations in the tissue play an important role in signaling whether CXCR4+ cells should stay in their present environment or migrate to other tissues. For instance, if local SDF-1 concentrations increase in response to a stimulus, CXCR4+ cells may follow the gradient to the SDF-1-rich environment. Similarly, static concentrations of SDF-1 will prevent the migration of CXCR4+ cells from the tissue; however, blocking the interaction of SDF-1 with CXCR4 results in rapid mobilization of stem cells and leukocytes into the peripheral blood.

CXCR4 is functionally expressed or overexpressed in a variety of solid tumor cancers, lymphoma, and chronic lymphocytic leukemia (Balkwill 2004; Peng et al. 2005). Within hypoxic areas of tumors, both SDF-1 secretion by fibroblasts and CXCR4 expression on tumor cells increase, which stimulate tumor cell growth, migration, and invasion. SDF-1 promotes tumor growth in a paracrine fashion by directly stimulating tumor cell proliferation and survival via CXCR4. Stromal cells in tissues such as bone, liver, and lungs secrete SDF-1, creating a concentration gradient that induces directional migration of CXCR4 expressing cancer cells toward these tissues (Kucia et al. 2005). Recently, CXCR4 was demonstrated to play a role in

cancer immunotherapy via T-cell mobilization and redistribution in the tumor microenvironment (Righi et al. 2011; Feig et al. 2013; Gil et al. 2014).

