Based on available PK/pharmacodynamic data from ongoing Study 1108 with doses ranging from 0.1 to 10 mg/kg Q2W or 15 mg/kg Q3W, durvalumab exhibited nonlinear (dose dependent) PK consistent with target-mediated drug disposition. The PK approached linearity at ≥ 3 mg/kg Q2W, suggesting near complete target saturation (membrane bound and sPD-L1), and further shows that the durvalumab dosing frequency can be adapted to a particular regimen given the linearity seen at doses higher than 3 mg/kg. The expected half-life ($t_{1/2}$) with doses ≥ 3 mg/kg Q2W is approximately 21 days. A dose-dependent suppression in peripheral sPD-L1 was observed over the dose range studied, consistent with engagement of durvalumab with PD-L1. A low level of immunogenicity has been observed. No patients have experienced immune-complex disease following exposure to durvalumab (further information on immunogenicity, please see the current durvalumab IB).

Data from Study D4190C00006 (Phase 1 trial in NSCLC patients using the combination of durvalumab and tremelimumab) also show an approximately dose-proportional increase in PK exposure for durvalumab over the dose range of 3 to 20 mg/kg durvalumab every 4 weeks (Q4W) or Q2W (further information on PK observations in Study 006, please see the current durvalumab IB).

The observed durvalumab PK data from the combination study were well in line with the predicted monotherapy PK data (5th median and 95th percentiles) for a Q4W regimen.

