Mitomycin-C or nitrosoureas	>42 days
Biologic agents (for example, antibodies)	≥2 weeks
Radiotherapy	≥4 weeks
Limited field radiotherapy	≥2 weeks
Major surgery, excluding biopsy	Patients with recent major surgery must have occurred >28 days prior to screening) must have recovered, in the opinion of the investigator, from the toxicity and/or complications from the intervention before starting therapy.
Study drug with an investigational product or nonapproved use of a drug or device	≥2 weeks

NOTE: At the discretion of the investigator, patients with hormone-refractory prostate cancer who are stable on gonadotropin-releasing hormone (GnRH) agonist therapy or patients with breast cancer who are stable on anti-estrogen therapy (for example, an aromatase inhibitor) may continue that treatment while enrolled in this study.

- [9] Have provided tissue from a newly obtained core or excisional biopsy of a tumor lesion or a recent biopsy defined by ≤3 years since last documented progression of disease. (Note: patients for whom newly obtained samples cannot be obtained such as in cases of inaccessibility or patient safety concern, an archived specimen can be submitted upon agreement from sponsor and if not restricted by local regulations.)

For ovarian expansion arm only: Be able to provide tissue (newly obtained core or excisional biopsy of tumor lesion) from an on-treatment biopsy for biomarker analysis.

- [10] Are male patients who are sterile (including vasectomy confirmed by post-vasectomy semen analysis) or agree use of an effective method of contraception and not to donate sperm or practice total abstinence from heterosexual activity, starting with the first dose of study treatment, during the study, and for at least 6 months following the last dose of study treatment, or longer, if determined by country requirements;
- [11] Female patients must either be of nonreproductive potential (ie, postmenopausal by history: ≥60 years old and no menses for ≥1 year without an alternative medical cause; OR history of hysterectomy, OR history of bilateral tubal ligation, OR history of bilateral oophorectomy) or must have a negative serum pregnancy test upon study entry.

- [12] Have an estimated life expectancy of ≥ 12 weeks, in the judgment of the investigator.
- [13] Capable and willing to learn to self-administer LY2510924, or have a caregiver who is willing to learn and able to administer LY2510924 by SQ injection.

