6.2.2. Definitions of Study Periods

Terms used to describe the periods during the study are defined below:

- **Baseline/Screening:** begins when the ICF is signed, and ends at the first study treatment (defined as receiving any study drug); if no study treatment is given, baseline/screening ends with the decision not to enroll. Lasts up to 28 days.
- **Study Period:** The overall study period for Study CXAD begins the day of the first patient's first dose of study treatment and ends at overall study completion (as defined in a bullet below).
 - **Study Treatment Period:** begins with the day of the patient's first study treatment and ends the day the patient and investigator agree that the patient will discontinue study treatment (discontinuation of assigned study drug(s); Section 6.3). Individual patients who enroll in Study CXAD may continue treatment until they have confirmed progressive disease or discontinued study treatment for any other reason.
 - **Post Discontinuation Follow-Up Period:** consists of the following phases:
 - **30-Day Short-Term (Safety) Follow-Up:** begins the day after the patient and the investigator agree that the patient will discontinue study treatment and ends with the short-term follow-up visit, to occur approximately 30 days thereafter.
 - **60-Day Short-Term (Safety) Follow-Up** begins the day after the 30-day follow-up visit and lasts approximately 30 days or approximately 60 days after the patient and the investigator agree that the patient will discontinue study treatment.
 - **90-Day Short-Term (Safety) Follow-Up** begins the day after the 60-day follow-up visit and lasts approximately 30 days or approximately 90 days after the patient and investigator agree that the patient will discontinue study treatment.
 - **Long-term Follow-up** begins the day after 90-day follow-up is completed and continues until the patient's death or end of trial (approximately every 12 weeks \pm 7 days the patient will be contacted).

- **Study Completion** for Study CXAD: occurs after the final analysis (occurring no more than 12 months after last patient enters treatment) and evaluation of the primary objective and secondary objectives have been performed. Investigators will continue to follow the Schedule of Events ([Attachment 1](#)) for all patients, until notified by Lilly that study completion has occurred.

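### Section 7.5.1 counts the end of contraception from the last durvalumab dose only, which for men can fall before the date inclusion criterion [10] requires and for women takes no account of daily LY2510924

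*Protocol*

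**What the plan says.** Protocol Section 7.5.1 gives the on-study contraception rules. Women of childbearing potential "must agree to continue using such precautions for 6 months following the last infusion of durvalumab", and "cessation of birth control after this point should be discussed with a responsible physician". Non-sterilized men are to use contraception "from Day 1 and for 6 months after receipt of the final dose of durvalumab". The section does not mention LY2510924 when it sets either end date.

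Inclusion criterion [10] in Section 6.1.2 covers men only. It requires contraception "for at least 6 months following the last dose of study treatment", with an allowance for longer periods under national rules. Criteria [11] and [17], which cover women, state no duration.

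Section 6.2.2 marks the end of screening by the "first study treatment (defined as receiving any study drug"), so in that place the term covers both drugs. The blood-donation rule in Section 7.5.1 is also tied to study treatment as a whole: "Patients should not donate blood while participating in this study or for 3 months after discontinuation of study treatment".

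**The concern.** The protocol gives men two end dates for the same obligation. The earlier one sits in the section that sites and patients would consult during treatment and follow-up. A site applying that section alone would release a man from contraception before the criterion under which he was enrolled permits.

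For women there is no second rule to fall back on. The single end date is tied to the drug given once per cycle, not to the one injected every day. The protocol itself gives a reason to take care with the daily drug: LY2510924 blocks CXCR4, and Section 5.5.1.1 says of the CXCR4/SDF-1 axis that "both are required for normal murine fetal development". Pregnancy testing after baseline is done only when clinically indicated (Attachment 1), so contraception carries most of the protection.

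What is at stake is one clear date for a reproductive-safety instruction. No sample size, dose-escalation rule or analysis depends on it.

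**Working it through.** The plan reports no figure for this gap, so there is nothing to reproduce. The check compares the rules and then counts days.

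**The rules side by side**

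- Men, [10]: at least 6 months from the last dose of study treatment. This reads as either drug, given the usage in Section 6.2.2.
- Men, Section 7.5.1: 6 months from the last durvalumab dose.
- Women, [11] and [17]: no duration.
- Women, Section 7.5.1: 6 months from the last durvalumab infusion, then a physician discussion with no date attached.

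**Inputs**

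- Cycle length: 28 days (Section 7.2.1).
- LY2510924: daily, Days 1 to 28 (Section 7.2.1.1).
- Durvalumab: Day 1 of each cycle only (Section 7.2.1.2).
- Durvalumab half-life at the relevant doses: "is approximately 21 days" (Section 5.6).
- Six months: taken as 183 days; the calendar range is 181 to 184.

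**Gap between last doses**

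If treatment ends on Day k of a cycle, with k from 1 to 28, the last LY2510924 dose falls k − 1 days after the last infusion. The smallest gap is 1 − 1 = 0 days and the largest is 28 − 1 = 27 days. Stopping one drug means stopping both (Sections 6.2 and 6.3.2), but this does not close the gap, because the dosing frequencies differ.

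**Contraception left after the last LY2510924 dose under Section 7.5.1**

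- Largest gap: 183 − 27 = 156 days (181 − 27 = 154 to 184 − 27 = 157).
- Shortfall against a full six months: 27 / 183 = 14.8%.

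**Is the period adequate for durvalumab itself?**

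183 / 21 = 8.7 half-lives, so the durvalumab anchor is reasonable for durvalumab. No corresponding calculation is possible for LY2510924, because the documents give no half-life or washout figure for it.

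**Gaps that need an extra assumption**

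- Durvalumab alone delayed by the one week that Section 7.2.5.3 permits, with LY2510924 continuing and treatment then stopping: 27 + 7 = 34 days, leaving 183 − 34 = 149 days (34 / 183 = 18.6% shorter).
- Durvalumab alone held for the full 12 weeks that Section 6.3.2 tolerates, with LY2510924 continuing: about 84 days if counted from the last infusion, or 27 + 84 = 111 days if counted from the missed Day 29 dose.

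Both cases need LY2510924 to continue past Day 28 before the next infusion, which no section states. Only the 0 to 27 days follows from the written schedule.

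**The case against.** The strongest reply is that nobody is left unprotected. A man who follows [10] meets both rules, so they are not impossible to satisfy together. A woman is covered from screening, through all dosing, and for about five months after her last LY2510924 injection, with a physician discussion to follow. Because both drugs stop together, the durvalumab date also limits how far LY2510924 exposure can run on. Anchoring to the longer-acting antibody is a defensible choice, and the murine statement does not show that 156 days is too short. The reading of study treatment as either drug is also inferred, since Section 6.2.2 defines the first treatment and not the last dose.

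Most of this stands, and it sets the size of the point. It does not remove it. Compatibility runs one way only: following [10] satisfies Section 7.5.1, but following Section 7.5.1 alone need not satisfy [10]. For women, the physician discussion supplies no date based on LY2510924.

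A reader might also infer that the shorter period is unsafe, or that the gap is routinely 34 days or more. The documents support neither: they contain no LY2510924 washout data, and the longer gaps rest on the assumption noted above. The blood-donation rule serves another purpose. It shows only that the section uses a study-treatment anchor elsewhere.

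A reader might further take the two menopause definitions as a serious eligibility defect. Criterion [11] asks for age 60 or older with a year of amenorrhea; Section 7.5.1 asks for 12 months at any age; [17] cites neither. The two may serve different purposes, namely the entry pregnancy test and on-study contraception. Eligibility is checked with the sponsor before enrollment (Section 7.3), and the number of women affected is not given. This is a harmonisation note only.

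**Conclusion.** The point holds as a minor one. For men, Section 7.5.1 is inconsistent with inclusion criterion [10], and the later date in [10] governs if both are to be met. For women, the only end date does not account for the drug given daily. On the stated schedule the difference is 0 to 27 days, leaving about 156 of 183 days after the last LY2510924 dose at the widest.

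This rests on two assumptions: that study treatment in [10] means either drug, which is the natural reading, and that six months is about 183 days. It is a correction for consistency and precaution. No hazard is demonstrated, and no statistical quantity changes.

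**What to change.** In Section 7.5.1, set the end of contraception for both sexes at 6 months after the last dose of LY2510924 or durvalumab, whichever is later. Carry over from [10] the allowance for longer national requirements. The rules for men then agree, and women have a date that covers both drugs.

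The cost is protocol wording and up to 27 more days of contraception on the ordinary schedule for patients whose last LY2510924 dose falls after the last infusion. Any matching consent wording should be checked; it is not among the documents reviewed.

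In the same edit, as optional tidying, have [17] state which definition of reproductive potential applies, and have [10] and [17] refer to the two-method requirement in Section 7.5.1, since both now speak of a single effective method.

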7.6. Treatment Compliance

7.6.1. LY2510924 Compliance

Patient compliance with LY2510924 will be assessed on Day 1 of each cycle (excluding Cycle 1). Compliance will be assessed by direct questioning, review of diary, and counting any returned vials. Deviations from the prescribed dosage regimen should be recorded on the CRF. On those study days that PK collection is scheduled (see [Attachment 1](#) and [Attachment 4](#)), patients will wait to self-administer LY2510924 until they are in the clinic.

For patients who are significantly noncompliant (<75% of expected study drug taken in a visit interval), investigative sites must counsel patients on the importance of study drug compliance and drug accountability. Patients who are consistently out of the compliance range may be discontinued after discussion with Lilly CRP or designee. A Lilly representative should be contacted upon the second instance of treatment noncompliance.

The following procedures will be employed to ensure appropriate drug accountability:

- Drug accountability will be emphasized at the start-up meeting.
- Drug accountability will be monitored throughout the study.

- Each patient should be instructed to return all study drug packaging and unused material to the study site at each visit. The study site will keep a record of all drug dispensed to and returned by the patients throughout the study. Study site personnel will return or destroy (as requested) all unused study drug for all patients.
- In the Phase 1a and 1b part of the study, patients will keep a study diary for the entire treatment duration to document that they are taking LY2510924 as prescribed.

